### *Validity of pregnancy and infant outcomes*

Although administrative claims data contain diagnosis and procedure codes to identify medically attended maternal and birth outcomes, the positive predictive value (PPV) of these codes varies by outcome, with the majority of PPVs for major congenital malformations ranging from 70-90® ([Andrade et al, 2013](#); [Cooper et al, 2008](#)). Algorithms to assess spontaneous abortion and stillbirths have also been developed, and those for stillbirth have shown high PPVs (99-100®) ([Likis et al, 2013](#))

#### **9.3.4.1 Case Validation Plan**

Validation will be conducted in the HIRD. Medical record/electronic health records will be sought to validate claims-identified outcomes for major congenital malformations, spontaneous abortion, still birth, and LMP. Similar to other pharmacoepidemiologic database validation studies, this validation study will provide estimates of positive predictive value (PPV) for each of the endpoints. In addition, a validation study of the algorithm to identify migraine cases and estimate the PPV of the algorithm will also be undertaken. Informed by the validation data for the migraine algorithm, sensitivity analyses will be conducted to restrict analyses to patients with an increased probability of having migraine (e.g., increased number and type of migraine diagnosis, treatments and specialist diagnoses) to assess any possible impact on results. The case validation plan will be described in detail in the Medical Record Plan (MRP).

Major congenital malformations will be adjudicated by a birth defects expert/clinical teratologist. Criteria to ascertain each individual malformation will be agreed upon in consultation with the experts, and classification will mirror groupings typically used by the Metropolitan Atlanta Congenital Defects Program (MACDP), noting that MACDP codes are not directly available in the HIRD. The same experts will also support development of abstraction forms for identification of covariate and outcome data and will adjudicate outcomes that are not clearly identifiable from the abstracted data. The two experts will independently review medical records that have been redacted of personally identifying information to determine outcome status. Disagreements will be resolved via discussion or review by a third clinician. Full details of the abstraction, redaction and review processes will be included in the MRP.

The medical records for the spontaneous abortion and still birth will be used to develop detailed case narratives. Medical records would be requested from providers and submitted to clinical experts for adjudication (blinded as to protected health information (PHI) and exposure status).

The medical record retrieval rate is about 60® but varies by study. Outcomes identified in claims where medical records are not available will be classified as provisional outcomes.

#### **9.4 Data Sources**

This study will use data from the MarketScan CCE databases and the HIRD. These databases contain fully adjudicated eligibility, pharmacy, procedure, and medical claims data for patients enrolled in large US health plans. The health plans provide coverage

for physician, hospital, and prescription drug services, and capture medical claims or encounter data from all available health care sites (inpatient hospital, outpatient hospital, emergency room, physician's office, surgery center, etc.) for virtually all types of provided services. The coding of medical claims conforms to insurance industry standards, including the use of designated claims forms (eg, physicians use the Health Care Financing Agency [HCFA]-1500 format and hospitals use the UB-92 format). Each record contains information on diagnoses (recorded using the International Classification of Diseases, Tenth Revision, Clinical Modification [ICD-10-CM]), procedures (recorded with ICD-10-CM procedure codes, Current Procedural Terminology [CPT] codes, or HCFA Healthcare Common Procedure Coding System [HCPCS] codes). Data are linked at the patient level by a unique identifier that is consistent across services, health plans, and time, and, so, patients can be tracked over multiple years even if they switch health plans. Claims for pharmacy services are typically submitted electronically by the pharmacy at the time prescriptions are filled. The following pharmacy claims data allow for longitudinal tracking of medication refill patterns and changes in medications used:

- National Drug Code (NDC) or HCPCS code
- Medication Brand Name
- Generic Classification
- Medication Strength
- Quantity Prescribed
- Days of Supply
- Fill Date

Undiagnosed conditions, and lifestyle and biometric factors (eg, smoking status) are not well captured in claims data. The data are Health Insurance Portability and Accountability Act (HIPAA) compliant and all data is anonymized.

The MarketScan CCE databases contain data on approximately 17 million employees and their dependents, annually, covered under a variety of fee-for-service and capitated health plans, including exclusive provider organizations, preferred provider organizations (PPOs), point of service plans, indemnity plans, and health maintenance organizations (HMOs).

The HIRD is a large administrative healthcare database maintained by HealthCore for use in health outcomes and pharmacoepidemiologic research. Health care utilization may be tracked for health plan members in the database back to January 2006. As of July 2019, there were 72.5 million unique individuals with medical coverage and more

than 51 million lives with both medical and pharmacy coverage. The HealthCore Integrated Research Environment (HIRE) has the ability to link the claims data in the HIRD to complementary data sources, including inpatient and outpatient medical records from healthcare providers submitting insurance claims, national vital statistics records, cancer and vaccine registries (state-by-state), disease and device registries, individual and provider surveys, point of care clinical data, and clinical oncology data.

#### **9.4.1 Review and Verification of Data Quality**

The MarketScan CCE databases are constructed through collection and standardization of raw data from the appropriate payers and linking files across time and data type to create a comprehensive and efficient set of database tables. Variables specific to particular employers are added, as are details on clinical information such as therapeutic class, generic product identifier, therapeutic group, etc. Other enhancements are made to improve the data quality and efficiency, for example: updating diagnosis and procedure codes to reflect changes in codes over time if necessary; creating a common synthetic patient identifier that enables patients to be tracked over time and across data types; integrating benefit plan characteristics, enrollment, outpatient pharmaceutical claims, and medical/surgical data, etc. A comprehensive series of edits on the reasonableness and validity of the data are conducted. For example, checking diagnosis against age and gender, checking charge against payment, checking zip codes, diagnosis and procedure codes against lists of valid values, etc. The verification of data quality follows MarketScan's standard operating procedures (SOPs), which are consistent with the International Society for Pharmacoepidemiology's Guidelines for Good Pharmacoepidemiology Practices. In particular, the SOPs in place prescribe that processes and deliverables are documented, reviewed, and validated in sufficient detail to allow for subsequent re-examination or replication. Data are collected when close to 100% of claims have been paid, which results in a lag time between date of service and date of payment of about six to nine months. No data editing, beyond what is applied in the database production process, will be employed for this study.

The HIRD has implemented the following processes to ensure the accuracy and validity of the data: (1) defining thresholds for completeness and accuracy of key data fields; (2) using per member per month (PMPM) calculations to understand and address emerging data trends (eg, changes in membership types and spend during the introduction of Affordable Care Act [ACA]); and, (3) in addition to the standard QC

checks, such as age and gender checks, the HIRD also undertakes payment and charge checks, address and zip codes checks, diagnosis and procedure codes checks, etc. Due to the HIRD 85® completeness inclusion criteria, the lag time between date of service and date of payment is 3 months. No data editing, beyond what is applied in the database production process described above, will be employed for this study.

The validation for the creation of analytic files from claims data typically involves a combination of a review of SAS program log and output files, independent coding, a review of program processes and documentation to ensure departmental SOPs are followed, and reconciliation of programming code with specifications. Individual programs are documented and revised as needed until sign-off by a validator using a validation/programming log.

### **9.5 Study Size**

Feasibility estimates for the years 2010-2014 indicate that annually we will be able to identify approximately 7,000 pregnant women with migraine from the MarketScan CCE database. In contrast, as of 2017, the HIRD included 11,704 pregnant women with migraine. Analyses will be conducted separately for each database and pooled if appropriate. The sample size calculations described below were based on estimates from the MarketScan CCE database, the smaller of the two databases.

We estimate that approximately 0.9® of pregnant women with migraine will be treated with a migraine preventive medication during pregnancy. Based on the projected uptake of erenumab-aooe in migraine patients, we estimate that from May 2018 through May 2027 approximately 1,400-1,500 pregnant women in the MarketScan CCE database with migraine will be exposed to erenumab-aooe during their pregnancy. The actual number will vary depending upon the utilization of erenumab-aooe treatment by the source population in the MarketScan CCE database.

Sample sizes for the comparison of the primary outcome (major congenital malformations) are calculated assuming a 3® prevalence of major congenital malformations in infants of women with migraine, a 62® live birth rates of pregnancies, 1:4 matching of the erenumab-aooe exposed to the comparator cohorts, and 80® power. In past studies in HIRD involving linkage of mothers and their infants, approximately 72-85® of completed pregnancies could be connected to a qualifying infant ([Mines et al, 2014](#); [Nkhoma et al, 2012](#)). In the MarketScan databases, the

mother-infant linkage is approximately 77%. The study will have at least 80% power to detect at least a 2-fold increase in the risk of major congenital malformations (Table 2).

**Table 2. Required Sample Size Estimates and Relative Risks for the Comparison of Major Congenital Malformations Between the Erenumab-aooe Exposed Cohort and the Unexposed Cohorts**

Relative Risk	Sample size of pregnant women in the exposed group, accounting for 62% live birth rate	Sample size of live births, accounting for a 77% mother-infant linkage rate	Sample size of live births in the exposed group
1.25	11,731	7,273	5,600
1.50	3,142	1,948	1,500
1.75	1,181	909	700
2.00	717	522	425
2.25	597	370	285
2.75	270	208	160
3.00	210	162	125

### 9.6.1.2 Final Analysis

The final analysis will be conducted at the end of the study period in November 2028 or when the study is determined to have been completed based on other criteria [REDACTED]. See [Section 9.6.2](#) for details of the final analysis.

## 9.6.2 Planned Method of Analysis

### 9.6.2.1 General Considerations

Each of the primary and secondary outcomes will be described using frequencies, proportions and corresponding 95% confidence intervals (CI). If there is sufficient sample size, formal comparisons to estimate risk (odds ratios (OR) and corresponding 95% CIs) will be undertaken, using inverse probability of treatment weights (IPTWs) to account for confounding. Demographic and baseline characteristics, and other covariates will be summarized by cohort of exposure. Discrete variables will be summarized using frequencies and proportions, and continuous variables will be summarized using means and standard deviation (SD) or medians and interquartile range (IQR), as appropriate.

### 9.6.2.2 Missing or Incomplete Data and Lost to Follow-up

The variables in this study will be measured by searching for diagnosis, procedure, and drug codes. Thus, the data will be captured to the extent that the MarketScan® CCE and the HIRD databases are appropriately populated with these codes. There will be no imputation of missing data. Covariates (eg, maternal race, alcohol use, smoking status) with extensive missing data will be described, but will not be included in regression models. The number of patients (women and infants) who are lost to follow-up when enrollment in the health plan ends will be described.

The use of medical records from HealthCore to confirm and validate the outcomes of interest as well as the timing of the pregnancy is a strength of this study; however, retrieval rates for requested medical records for mothers and/or infants will be less than 100%. We will provide a description of the patients who were excluded due to inability to obtain medical records and their characteristics based on the administrative claims. Additional discussion of the medical records procurement will be described in detail in the MRP.

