### 9.3.3 Covariate Assessment

Study cohorts will be described according to baseline covariates. Demographic attributes will be determined on the cohort entry date while others will be assessed during the baseline period, unless otherwise specified. All covariate information will be ascertained through inpatient and/or outpatient claims for diagnoses and procedures, and through pharmacy claims utilizing ICD-10 CM for diagnoses; ICD-10 PCS, CPT, or HCPCS codes for procedures; and GPI or NDC codes for dispensings. Additional details will be provided in the Statistical Analysis Plan (SAP) and the Medical Record Plan (MRP).

Covariates to be assessed include the following:

- Maternal age at estimated LMP (in years)

- Maternal race, if available

- Calendar year at estimated LMP

- Geographic region of health plan

- Migraine characteristics (eg, migraine with aura, chronic migraine)

- Comorbid conditions at baseline (eg, chronic hypertension, hyperlipidemia, diabetes, polycystic ovarian syndrome, hypothyroidism, hyperthyroidism, depression, anxiety, epilepsy), identified through ICD-10-CM diagnosis codes

- Medications in the baseline period (eg, acute and preventive migraine treatments, other treatments not for migraine, suspected teratogenic medications), identified through NDC codes or HCPCS codes

- Adverse events during pregnancy (eg, pre-eclampsia, gestational diabetes), identified through ICD-10-CM diagnosis codes

- Concomitant medications with claims after or a days supply that overlaps the LMP date and by trimester during the pregnancy (eg, acute migraine treatments, other treatments not for migraine, suspected teratogenic medications), identified through NDC codes or HCPCS codes

- History of obstetric outcomes (eg, prior pregnancies, multiple gestation, outcomes of prior pregnancies including spontaneous abortions) using all available history

- Use of prenatal testing

- Resource utilization (eg, number of prenatal visits, types of providers visited, emergency department visits)

- Body mass index, if available

- Alcohol, tobacco, and substance abuse, if available

Exposure to infections during pregnancy, if available  
 Previous history of congenital malformations, if available

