#### 9.6.2.4 Analysis of the Primary, Secondary, and Exploratory Endpoint(s)

##### 9.6.2.4.1 Analysis of the Primary Endpoint

Frequencies and the proportions (95% CIs) of major congenital malformations, in infants born to the following three cohorts of women with migraine, will be estimated: (1) those exposed to erenumab-aooe immediately prior to or during pregnancy, (2) those exposed to other preventive migraine medications immediately prior to or during pregnancy, and (3) those unexposed to any migraine preventive medications, including erenumab-aooe.

If there is sufficient sample size and adequate overlap in the distribution of confounding variables, formal comparisons to estimate odds ratios and corresponding 95% CIs will be undertaken. We will use inverse probability of treatment weights to address confounding. We will fit a logistic regression model for the conditional probability of treatment,  $Pr(A_i = a|L_i)$ , where  $L_i$  is a vector of measured baseline confounders of the exposure and the outcome. The conditional probability of treatment given a set of covariates is commonly referred to as the propensity score (PS), and a histogram of the overlap in the propensity score will be presented. IP of treatment weights will be constructed as:

$$\widehat{W}_i^2 = \frac{1}{\widehat{Pr}(A_i = a|L_i)}$$

For the analyses described here,  $L_i$  will be based on subject-matter knowledge (see covariates identified in [Section 9.3.3](#)).

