#### **9.8.1.3 Confounding**

Confounding by baseline covariates will be addressed with the use of inverse probability of treatment weights. We rely on subject matter knowledge to include candidate confounding variables in our analyses, but residual confounding may exist as a result of unmeasured or incomplete confounders (eg, obesity, use of alcohol, smoking, illicit drug use) or unknown confounders. We will include even weak confounders in the final analysis, sacrificing precision of our final effect estimates by guarding against the potential bias that might be introduced by omission of the confounder. The approach to address unmeasured confounders is addressed in [section 9.8.4](#).

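### Dropping poorly recorded covariates, with smoking and alcohol named, from the regression models is unreconciled with the aim of including even weak confounders and leaves the primary odds ratio less adjusted than the recorded data allow

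*Protocol*

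**What the plan says.** All references are to the Protocol.

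- **Section 9.6.2.2** notes that study variables are measured by searching for diagnosis, procedure and drug codes. It then says "There will be no imputation of missing data" and "Covariates (eg, maternal race, alcohol use, smoking status) with extensive missing data will be described, but will not be included in regression models".
- **Section 9.6.2.4.1** builds the treatment weights for the primary comparison: "We will fit a logistic regression model for the conditional probability of treatment". The confounder vector "will be based on subject-matter knowledge (see covariates identified in" Section 9.3.3.
- **Section 9.3.3** lists the covariates, among them "Maternal race, if available" and "Alcohol, tobacco, and substance abuse, if available". Body mass index carries the same condition.
- **Section 9.8.1.3** says "We will include even weak confounders in the final analysis, sacrificing precision of our final effect estimates", with the stated purpose of guarding against bias from leaving a confounder out. The sentence before it concedes that "residual confounding may exist as a result of unmeasured or incomplete confounders (eg, obesity, use of alcohol, smoking, illicit drug use".
- **Section 9.8.1.1** accepts that completeness or sensitivity may be low for body mass index, alcohol, tobacco and substance abuse. Section 9.6.2.5.3 lists quantitative bias analyses for residual confounding and misclassification as something to be explored.

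**The concern.** A covariate chosen on subject-matter grounds as a confounder can be removed from the adjustment because of how well it is recorded, whatever its relation to treatment and outcome. That sits badly with a plan that elsewhere gives up precision to avoid omitting confounders.

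The trigger is also the wrong one for this data source. A claims history either contains a tobacco or alcohol code or it does not, so the derived indicator has a value for every woman. Its weakness is that many true smokers have no code. That is misclassification, and it calls for a different remedy from a blank field. Where such a code is specific, conditioning on it removes part of the confounding; leaving it out removes none.

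At stake is the adjusted odds ratio for major congenital malformations against each comparator group, and by Section 9.6.2.4.2 the secondary comparisons too. If exposed and comparator women differ in these factors, the estimate carries bias that the data could have reduced. The exploratory bias analysis comes afterwards and does not alter that estimate.

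**Working it through.** **Does the rule reach the primary estimate?** Yes. Section 9.6.2.2 speaks of regression models without limitation. Section 9.6.2.4.1 makes the propensity score a logistic regression on the 9.3.3 covariates. A covariate barred from that model does not enter the weights.

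**Do 9.6.2.2 and 9.8.1.3 agree?** One selects on completeness of recording, the other on confounding strength. They are not logical opposites, but a poorly recorded confounder falls under both, and neither section says which governs. Section 9.8.1.3 refers to 9.8.4 for the approach to unmeasured confounders; 9.8.4 covers only outcomes missed when enrollment ends.

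**How large could the effect be?** The protocol gives no prevalence, effect size or code sensitivity for these factors, so there is no plan figure to reproduce. Every confounder input below is assumed, with no true drug effect.

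*Omitted binary confounder.* With prevalence p1 in the exposed, p0 in the comparator and confounder-outcome risk ratio R:

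spurious RR = (1 + p1(R − 1)) / (1 + p0(R − 1))

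- Smoking 20% vs 10%, R = 2: 1.20/1.10 = 1.091; ln 1.091 = 0.087. Against the plan's target ratio of 2.0, 0.087/0.693 = 13% on the log scale.
- Smaller imbalance, 15% vs 10%, R = 1.3: 1.045/1.030 = 1.015.
- Reversed imbalance, 5% vs 10%, R = 2: 1.05/1.10 = 0.955. The direction depends on which group has the higher prevalence.

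*After adjusting for an imperfect code.* Take 99% specificity and stratify on code recorded or not. At 50% sensitivity (smoking 20% vs 10%, R = 2; risks relative to a non-smoker):

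| Stratum | Exposed: share with code status | Exposed: relative risk | Comparator: share with code status | Comparator: relative risk | Stratum RR |
|---|---|---|---|---|---|
| Code recorded | 0.20×0.5 + 0.80×0.01 = 0.108 | 1 + 0.100/0.108 = 1.926 | 0.10×0.5 + 0.90×0.01 = 0.059 | 1 + 0.050/0.059 = 1.847 | 1.042 |
| Not recorded | 0.892 | 1 + 0.100/0.892 = 1.112 | 0.941 | 1 + 0.050/0.941 = 1.053 | 1.056 |

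The Mantel-Haenszel RR over the two strata is 1.054. The same steps at 30% and 70% sensitivity give 1.071 and 1.036. The code therefore removes roughly 20%, 40% and 60% of the log-scale bias at 30%, 50% and 70% sensitivity.

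*Obesity, if obesity codes are used.* For 35% vs 20% with R = 2, the crude value is 1.35/1.20 = 1.125; a code with 98% specificity and 30/50/70% sensitivity leaves 1.102/1.080/1.054. With R = 1.3, 1.105/1.060 = 1.042 falls to 1.035/1.027/1.019.

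**Against sampling error.** Take the 425 exposed live births in Table 2 for a relative risk of 2.00, 1:4 matching (1,700 comparators) and 3% risk in both groups, giving 12.75 and 51 events:

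SE(log OR) = √(1/12.75 + 1/412.25 + 1/51 + 1/1649) ≈ 0.32

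The bias recovered for smoking is ln(1.091/1.071) = 0.018 to ln(1.091/1.036) = 0.052. The largest recovery in any scenario here is ln(1.125/1.054) = 0.065. These are about 0.06, 0.16 and 0.2 of a standard error.

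**The case against.** The strongest reply is that the plan is coherent: use what is adequately captured and disclose the rest. The commitment in 9.8.1.3 concerns weak confounders, not poorly recorded ones, and the sentence before it sets alcohol, smoking and obesity apart as unmeasured or incomplete. Section 9.3.3 makes these covariates conditional on availability, 9.8.1.1 discloses the weakness, and bias analysis is foreseen. This stands to the extent that a reader who infers a flat contradiction goes further than the text. It is a tension that the protocol leaves unresolved.

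A second reply is that, if a code-based variable is never missing, the rule never bites on it. That does not rescue the rule, because 9.6.2.2 itself names alcohol use and smoking status as examples of what would be excluded.

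Other inferences are tempting but unsupported:

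- **All three named covariates will be dropped.** Exclusion is conditional on extensive missing data, and race, alcohol and smoking are examples. The cut-off may properly sit in the SAP and is no defect here.
- **Obesity or body mass index is excluded.** Section 9.6.2.2 names neither; the obesity figures apply only if the rule is extended to it.
- **Women with missing values will be discarded.** The protocol rules out imputation but nowhere specifies a complete-case analysis.

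It is also fair that an insensitive code adjusts incompletely: at 30% sensitivity, about four fifths of the assumed bias remains.

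**Conclusion.** The point holds as a choice of method that should be changed. Followed as written, 9.6.2.2 can keep recorded confounder information out of the propensity model for a reason that does not suit code-based variables, and the protocol does not reconcile this with the aim in 9.8.1.3. Disclosing residual confounding is no reason to leave out measurements that would reduce it.

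The consequence is modest. On the assumed smoking scenario the spurious RR is 1.09, falling to about 1.07-1.04 with the code in the model; with a small imbalance the whole bias is about 1.5%. The recoverable part is at most about 0.065 on the log scale in the scenarios shown, against a standard error near 0.3. A reader might infer that the primary result would be seriously distorted. The documents give no prevalence, effect size or sensitivity to support that, and the sign of the bias is not known in advance.

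**What to change.** Amend Section 9.6.2.2 so that tobacco, alcohol and substance-abuse codes, and obesity codes if used, enter the propensity model as recorded/not-recorded indicators, however infrequent. Report their standardized mean differences with those of the other covariates. Add race and body mass index with an explicit unknown category as a sensitivity analysis; that device is more debatable and need not be in the primary model. State in 9.8.1.3 that this is how incomplete confounders are handled, and correct its reference to 9.8.4.

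The cost is a few sentences in the protocol, matching text in the SAP, a few more propensity-model terms and one sensitivity analysis, with no new data. Adjustment by an insensitive code remains incomplete, so the stated limitation and the bias analysis should stay, and the weights will be slightly more variable.
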